Through completion of Aims 1 and 2, we have: 1) validated the ASD phenotype within a sample of individuals with PMS, 2) established electrophysiological biomarkers of PMS, and 3) used biomarkers associated with PMS to identify an overlapping subset in iASD. In Aim 3, we will evaluate the feasibility of our biomarkers in a clinical trial with rhGH. Results will demonstrate evidence of our biomarkers' utility for: 1) stratifying subsets within iASD, 2) detecting target engagement with rhGH via neural responses, and 3) predicting treatment responders based on electrophysiological profiles. We have demonstrated feasibility of our biomarkers in individuals with ID who are minimally verbal, and this study will specifically focus on this underserved population in ASD research. *Upon successful completion of the proposed research*, we expect to clarify an underlying neural mechanism in PMS common to subsets of iASD, validate methods to predict treatment response for future clinical trials, and demonstrate efficacy of rhGH for individuals with PMS and iASD with glutamatergic dysfunction.

Innovation

To date, the development of treatments in ASD has mainly relied on strategies only loosely related to what is known about the neurobiology, using etiologically heterogeneous samples, and delivering intervention broadly and with mixed success. More recently, genetic discovery and model systems have elucidated the neurobiology of several subtypes of ASD, including PMS, and led to opportunities for developing biomarkers and novel therapeutics. *This proposal is innovative, in our opinion, on several technical and conceptual levels.* First, this study will leverage existing work in animal models of PMS and include electrophysiological tests. Second, we have the largest known cohort of individuals with PMS and have identified both a unique clinical phenotype and a striking VEP deficit that characterizes this population. Thus, we are uniquely situated to systematically assess the reliability of both clinical and electrophysiological measures in PMS. Third, the phenotype and electrophysiological profile identified in PMS is critically relevant to ASD. We will use the knowledge gained in an ASD-related syndrome to inform stratification of a subset

Figure 6. Children with PMS show significant improvement in sensory symptoms following 12 weeks of treatment with IGF-1. Greatest improvement was noted in the hyporeactivity domains ($n=6$);

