Research Design. The proposed intervention will recruit 15 children with PMS and 15 children with iASD (2-12 years old). Treatment will follow a randomized, placebo-controlled, crossover format with 12 weeks in each treatment phase (rhGH and placebo). This duration was selected based on evidence with IGF-1 in PMS suggesting our clinical outcomes will be sensitive to change within this time frame (Kolevzon et al., 2014). The primary electrophysiological outcomes will be VEP gamma band activity as our preliminary data with PMS in IGF1 suggests it is sensitive to drug effects (Fig. 5). The primary clinical outcome will be the SAND because: a) our preliminary studies suggest improvement on this measure following IGF-1 (Fig. 6), b) it accurately reflects a sensory phenotype characteristic of PMS and is relevant to a substantial subset of iASD, c) it is associated with electrophysiological measures, and d) it has been validated in ASD and ID.

Inclusion criteria: All participants with PMS will have pathogenic *SHANK3* deletions or sequence variants confirmed in clinical genetics laboratories approved by the Clinical Laboratory Improvement Amendments (CLIA). Genotyping will also be used to confirm the absence of known pathogenic copy number variants in the iASD group. Participants with iASD will meet gold standard diagnostic criteria for ASD, confirmed by the Autism Diagnostic Observation Schedule – 2nd Edition (ADOS-2; Lord et al., 2012) and the Autism Diagnostic Interview-Revised (ADI-R; Lord et al., 1994). All iASD subjects will have a reduced neural response defined by $P_{60}-N_{75}$ amplitudes within one standard deviation of the PMS mean. Subjects will be on stable medication and psychosocial treatment regimens for at least three months prior to enrollment.

Exclusion criteria: 1) closed epiphyses; 2) active or suspected neoplasia; 3) intracranial hypertension; 4) hepatic insufficiency; 5) renal insufficiency; 6) cardiomegaly/valvulopathy; 7) allergy to growth hormone or any component of the formulation; 8) comorbid conditions which prevent participation; 8) visual problems which preclude use of VEP.

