Data Analysis. Following the procedures of a 2x2 cross-over design, each subject is randomized to one of two treatment sequences. First we will use graphical and numerical statistics to characterize treatment-, period- and cross-over effects (Jones & Kenward, 1989). Under the assumption of no cross-over effects and data following an approximate normal distribution, we will fit generalized linear mixed models (GLMMs) to the data examining the effects of group (PMS, iASD), condition (placebo, drug), time (baseline, week-12). Interactions on clinical and VEP measures will be checked for differential treatment effects, including subject level random

intercepts, to control for within subject correlations. Next, we will add baseline VEP gamma band activity, along with its interactions, to the models for clinical outcomes. In particular, a VEP by group by time interaction would suggest that the electrophysiological marker is predictive of differential treatment response. We will repeat these analyses with secondary electrophysiological markers and any derived composites. To examine whether electrophysiological markers track changes in clinical profiles, we will fit an additional GLMM with VEP values included as a time-varying rather than baseline covariate. If treatment effects become less significant it will suggest that rhGH is acting on clinical outcomes through the biomarker. Finally, we will directly correlate week-12 change scores for EEG and clinical measures. In case of major cross-over effects, we will base our primary analysis on phase 1 data only as a parallel group study. All tests will use a two-sided α of .05.

Power Analysis: Power is calculated for drug group differences in baseline to week 12 change scores in VEP gamma power since we are primarily interested in an overall treatment effect rather than a differential effect by group. These correspond to paired t-tests, taking advantage of the crossover design. With α at .05, we have 80% power to detect moderate to large effects ($d=.77$ within each group, $d=.53$ across groups), a reasonable expectation based on the potentially disease modifying effects of IGF-1 and our pilot study, which found a large effect ($d=1.05$) of IGF-1 in PMS on a different primary outcome (ABC-SW).

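### The claim that a VEP marker predicts treatment response has no deciding test: several marker–outcome pairs are each tested at .05, and composites are left undefined

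*Combined protocol and SAP*

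**What the plan says.** The section on the significance of the expected contribution says the results will show biomarker utility for, among other things, "predicting treatment responders based on electrophysiological profiles", and that the project expects to "validate methods to predict treatment response for future clinical trials". The Introduction to Aim 3 lists two purposes: detecting change in neural response, and predicting clinical responders.

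Under Outcome measures, the primary VEP outcome is magnitude-squared coherence (MSC) at 30–36 Hz, and one secondary VEP outcome is named, the P60-N75 amplitude. The primary clinical outcome is SAND hyporeactivity. ABC-SW and the other measures in Table 1 (Clinical Outcome Measures) share a single heading as secondary and exploratory.

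The Data Analysis paragraph enters baseline gamma and its interactions into the clinical-outcome models. It treats a VEP by group by time interaction as the sign of a predictive marker. It continues: "We will repeat these analyses with secondary electrophysiological markers and any derived composites". A model with VEP as a time-varying covariate follows, and then: "Finally, we will directly correlate week-12 change scores for EEG and clinical measures". It closes: "All tests will use a two-sided α of .05". It contains no multiplicity adjustment, order of testing, exploratory label or composite formula.

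**The concern.** Prediction of response is a stated purpose, described in the language of validation, yet the plan does not say which result would establish it. As written, a significant interaction for either marker, for a composite, or on any clinical outcome could be reported as a predictive marker. Each test carries a 5% error rate, but the claim as a whole carries more. Because the result is intended to guide later trials, a chance finding could send them after the wrong marker or the wrong patients.

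The stated criterion has a second weakness. The same paragraph defines group as PMS or iASD and condition as placebo or drug. A VEP by group by time term therefore asks whether the marker relates to change differently in the two diagnoses. It does not ask whether the marker modifies the drug effect.

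**Working it through.** **Inputs.** "The proposed intervention will recruit 15 children with PMS and 15 children with iASD (2-12 years old", so n = 30. Alpha is .05 two-sided for every test (Data Analysis). The named markers are two: 30–36 Hz MSC and P60-N75 (Outcome measures). The clinical outcomes are SAND hyporeactivity (primary), ABC-SW (the only other measure named in the text before the reference to the table), and the nine instrument rows of Table 1 (1 social, 3 language, 4 repetitive behavior, 1 adaptive).

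**Step 1. The plan's own figure.** It states that "we have 80% power to detect moderate to large effects ($d=.77$ within each group, $d=.53$ across groups" and "These correspond to paired t-tests, taking advantage of the crossover design". Exact noncentral-t power, with noncentrality d√n:
- n = 15, d = .77: .77 × √15 = 2.98, power 79.2% (80% needs d = .778).
- n = 30, d = .53: .53 × √30 = 2.90, power 80.1% (80% needs d = .529).

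The figures reproduce. They cover the overall drug effect on gamma only. No power or error rate is given for prediction or tracking.

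**Step 2. Independent tests.** P(at least one false positive) = 1 − .95^m.
- One pair, m = 1: 5%.
- 2 markers × 2 outcomes, m = 4: 1 − .95⁴ = 18.5%; expected false positives 4 × .05 = 0.2.
- 2 markers × 9 rows, m = 18: 1 − .95¹⁸ = 60.3%; expected false positives 18 × .05 = 0.9.

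**Step 3. Correlated tests.** The documents give no correlations among markers or among outcomes, so a range is assumed. Simulation: 20,000 runs, n = 30, normal data, equal correlation rho among markers and among outcomes, no true marker–outcome relation. A test is positive if |r| > t/√(28 + t²), where t = 2.048, so |r| > .361. Entries are the percentage of runs with at least one false positive.

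| Family | rho 0 | .3 | .5 | .7 | .8 |
|---|---|---|---|---|---|
| 1 × 1 | 5.1 | 5.0 | 5.2 | 4.8 | 4.8 |
| 2 × 2 | 18.5 | 17.8 | 16.5 | 13.6 | 12.3 |
| 2 × 9 | 59.6 | 53.9 | 44.4 | 32.1 | 25.3 |

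Composites are not counted, nor are the subscales within rows.

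**Step 4. Why one named test rather than an adjustment.** Bonferroni over 18 tests needs .05/18 = .0028. The correlation detectable with 80% power at n = 30 is tanh[(z for alpha + .842)/√27]. At .05 this is about .49; at .0028 it is about .63. With 30 children, spreading alpha is costly, while naming one test keeps the error at 5%.

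**The case against.** **The trial is small and framed as feasibility.** The safety section calls it exploratory, the Power Analysis puts the overall treatment effect first, and the Data Analysis says only that an interaction would suggest prediction. Unadjusted secondary biomarker tests are common in such trials. This stands as far as severity goes. It does not remove the gap, because the Data Analysis labels none of these tests exploratory and the significance section promises validated prediction methods.

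**A lead pair is already implied.** Gamma is the primary VEP outcome and is entered first, SAND hyporeactivity is the primary clinical outcome, and the aims and Expected outcomes link gamma to sensory measures. This is true, and it makes the remedy short. But these are an expectation and two separate designations; nowhere is that pair made the deciding test.

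**The nine rows are not equal claims.** All except the SAND already carry the secondary and exploratory heading, Vineland appears twice, and the SAND is itself one of the rows. For that reason the 2 × 2 reading is shown alongside.

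**The simulated test is not the planned mixed model.** Agreed. It stands in for a family of tests that each hold 5%, so the figures are approximate.

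**Stronger readings that the documents do not support.** A reader might count all 11 extracted VEP variables (6 bands, 2 amplitudes, 3 latencies) against 9 rows and arrive at 90% at rho .5. That list describes signal extraction. Only P60-N75 is named as secondary, and nothing places the other variables in the prediction models. A reader might also conclude that composites will be built after the results are seen. The plan is silent on when they are formed, and silence does not show that.

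**Conclusion.** The point holds as a gap in how the prediction claim is decided. The false-positive chance is about 12–18% on the narrow reading and about 25–60% on the broader one, instead of 5%. These figures assume 30 complete children, normal data, no true relation, equal correlations between 0 and .8, and each test holding its nominal level.

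A reader might infer that a false predictive marker is likely, or is the expected result of this trial. The documents do not support that: on the 2 × 2 reading the chance stays below 20%, and on the 2 × 9 reading it passes one half only at the lower correlations. The primary drug-effect analysis and its power statement are unaffected. This is a cheap improvement.

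**What to change.** In the Data Analysis paragraph:
- Name one deciding prediction test: baseline 30–36 Hz MSC by treatment condition (drug versus placebo) by time, on SAND hyporeactivity, two-sided .05. State that it replaces the VEP by group by time criterion, which omits treatment condition.
- Label all other marker-by-outcome interactions, the time-varying models and the change-score correlations exploratory. Report them with estimates, 95% confidence intervals and the number of tests run.
- Fix the formula of any composite before unblinding, or keep composites out of inferential claims.

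In the significance section, tie the prediction and validation wording to that one test.

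The cost is a few sentences, with no added data, visits or patients. The small downside is that a relation seen only for another marker or outcome can be reported only as hypothesis-generating.

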both demonstrate the characteristic waveform, VEP amplitudes are significantly smaller in iASD for both P_{60} - N_{75} ($p=.005$) and N_{75} - P_{100} ($p=.009$; Fig.3). Moreover, results from frequency domain analyses indicate that children with iASD showed significantly weaker activity in the 30-36 Hz range ($p<.01$) and 38-48 Hz range ($p=.034$), corresponding to gamma band activity. **Cognitive ability has no effect on the results.** In PMS, we see distinct VEP waveforms with smaller P_{60} - N_{75} amplitudes reflecting deficits in glutamatergic activity (Fig. 2B & 3). All PMS participants displayed reduced excitatory responses (absence of P_{60} - N_{75}), compared to both TD and iASD (p 's $<.001$). Across groups, reduced P_{60} - N_{75} amplitude corresponded to greater sensory hyporesponsiveness on the SAND ($n=32$, $r=-.529$, $p=.001$) and SSP ($n=32$, $r=.403$, $p=.022$), suggesting VEP response marks variability in clinical symptoms. P_{60} - N_{75} amplitude also correlated with *SHANK3* deletion size ($\rho = .414$; Fig.3 inlay) where there was significantly reduced amplitude in patients with larger deletions as compared to point mutations in

[figure not shown]

Figure 3. PMS shows significantly smaller VEP amplitudes relative to TD and iASD. Inset: P_{60} - N_{75} amplitude is further reduced with increased size of *SHANK3* deletion.

SHANK3 ($p=.03$). Yet, all patients with PMS display the expected GABAergic positive peak at P_{100} , indicating a specific, dissociable, glutamatergic VEP signature. These results are consistent with work in animal (Bozdagi et al., 2010) and human neuronal (Shcheglovitov et al., 2013) model systems demonstrating the deleterious effects of *SHANK3* deficiency on glutamatergic system function. In an effort to examine the use of VEPs as a stratification biomarker to aid personalized medicine approaches among an otherwise heterogeneous group of children with iASD ($n=27$), our results suggest that approximately 30% display P_{60} - N_{75} amplitudes within one standard deviation of the PMS mean (Fig.4; purple iASD circles below red dotted line), reflecting “PMS-like” excitatory

deficits.

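### The model for whether VEP tracks clinical change does not separate within-child movement from stable differences between children

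*Combined protocol and SAP*

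**What the plan says.** Data Analysis (Approach, Aim 3) fits GLMMs with group, "condition (placebo, drug), time (baseline, week-12") and subject-level random "intercepts, to control for within subject correlations". The tracking question then gets its own model: "To examine whether electrophysiological markers track changes in clinical profiles, we will fit an additional GLMM with VEP values included as a time-varying" covariate instead of a baseline one. No centring of VEP, no within/between split and no random slope is mentioned. The only stated reading of this model is that a treatment effect losing significance would point to rhGH working through the biomarker. A direct correlation of week-12 EEG and clinical change scores follows. On error control: "All tests will use a two-sided α of .05".

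Scientific Premise for Aim 3 reports, across groups, that reduced P60-N75 "amplitude corresponded to greater sensory hyporesponsiveness on the SAND ($n=32$, $r=-.529$, $p=.001"), and a correlation of .403 with the SSP. Under Outcome measures, gamma-band MSC is the primary VEP marker and P60-N75 amplitude the secondary one; both VEP and clinical measures are collected at four visits in each phase.

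**The concern.** A random intercept models correlation among a child's residuals. It does not remove stable child differences from a time-varying covariate. Entered as it stands, VEP carries two associations: children with low VEP have worse scores, and a child's score moves when that child's VEP moves. Only the second is tracking.

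The first was seen before the trial. The model could thus give a non-zero VEP coefficient, and some attenuation of the treatment effect, even if no child's score ever followed that child's VEP. Whether VEP follows clinical response is a central biomarker question of Aim 3 (see also Expected outcomes), so it matters which association the model reports.

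**Working it through.** **The plan's own figure.** The plan gives no error rate for the tracking model. Its one computed figure is power: "we have 80% power to detect moderate to large effects ($d=.77$ within each group, $d=.53$ across groups"), with the note "These correspond to paired t-tests, taking advantage of the crossover design". With noncentrality d√n:
- n = 15: .77 × √15 = 2.98, 14 df, critical t 2.145, power 79.2%.
- n = 30: .53 × √30 = 2.90, 29 df, critical t 2.045, power 80.1%.

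The stated power reproduces. It concerns the treatment effect on VEP and does not bear on tracking.

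**Inputs.**
- Sample: "15 children with PMS and 15 children with iASD (2-12 years old"), each child in both phases (Research Design).
- Records per child: 4 if only baseline and week 12 of each phase are modelled, 8 if all visits are used.
- Stability: SAND test-retest ICC .82-.97 (Scientific Premise); VEP amplitude test-retest correlation above .93 (Figure 2), which is not an ICC for gamma MSC.
- Between-child r: -.529 as reported, with -.2 and -.3 as assumed weaker values.

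**Why the coefficient is a mixture.** Scale both measures to unit variance, with m records per child, VEP ICC ρx and SAND ICC ρy. Ignoring the other fixed effects, and the part of the child variance that VEP explains:

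β ≈ (1-λ)β_within + λβ_between, with λ = ψB/(W + ψB), W = (m-1)(1-ρx), B = mρx + (1-ρx), ψ = (1-ρy)/[(1-ρy) + mρy].

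Example, both ICCs .7 and m = 4:
- ψ = .3/(.3 + 2.8) = .0968; W = 3 × .3 = .90; B = 2.8 + .3 = 3.1; ψB = .30.
- λ = .30/1.20 = .25, so a quarter of the weight falls on the between-child association.
- At r = -.529, β_between = -.529 × .7/(.7 + .3/4) = -.478.
- With β_within = 0, the expected coefficient is .25 × (-.478) = -.12, not zero.

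**Simulation.** 30 children, 2x2 crossover, zero within-child association, r between stable child levels. The fit is a REML random-intercept model with group, condition, time, their interactions, period and undivided VEP, with 1,500 trials per cell. Monte Carlo standard error is √(.05 × .95/1500) = 0.6 points near 5% and at most √(.25/1500) = 1.3 points. Rejection of the VEP coefficient at .05, in %:

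| VEP ICC | SAND ICC | λ (m=4) | r=-.529, m=4 / m=8 | r=-.30, m=4 / m=8 | r=-.20, m=4 / m=8 |
|---|---|---|---|---|---|
| .70 | .90 | .09 | 13 / 9 | 9 / 6 | 6 / 6 |
| .93 | .97 | .12 | 19 / 11 | 11 / 7 | 7 / 7 |
| .70 | .70 | .25 | 33 / 17 | 13 / 10 | 8 / 8 |
| .82 | .82 | .25 | 32 / 19 | 14 / 9 | 9 / 6 |
| .93 | .90 | .33 | 46 / 27 | 15 / 11 | 10 / 8 |
| .93 | .82 | .48 | 57 / 42 | 20 / 17 | 12 / 11 |

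At r = -.529 with 4 records the rates broadly rise with λ. With no between-child correlation the rate is 4-8%, nominal within simulation error, so the between-child association is the cause.

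**Alternatives under the same null.** In eight further scenarios, with -.529 read as the observed single-visit correlation, the undivided term rejected in 13-73% of trials. The within-child deviation term rejected in 4.0-5.9%, and a change-score correlation in 4.0-6.4%.

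**Treatment-effect shrinkage.** Let rhGH raise VEP by 0.5 SD and, independently, improve the score by 0.4 SD (r = -.529, both ICCs .7, 4 records). The expected shift from adding VEP is -.12 × 0.5 = -.06. In simulation the mean treatment estimate moved from -.39 to -.33 and shrank in 87% of trials. With VEP split it stayed at -.40 and shrank in 49%.

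**The case against.** - **The plan already has a within-child analysis.** The week-12 change-score correlation removes stable child differences and holds about 5%. A reader might infer that the plan has no valid answer to the tracking question; that would be wrong. What remains is that the model built for the question is the mixed one, and nothing says which result decides.
- **No rule is stated for the VEP coefficient.** A reader might infer that the plan will declare tracking when this coefficient is significant. The text does not say so, and the rejection rates belong to that inferred test. However, the treatment-effect reading that the plan does state passes through the same coefficient.
- **The -.529 may not carry over.** It concerns P60-N75, not gamma MSC, and was pooled across groups, so part of it may be a group difference that the model's group term would absorb. The iASD children are also selected on low P60-N75 (Inclusion criteria), which may weaken it further. All of this stands and argues for weight on the -.2 to -.3 columns. The tracking sentence speaks of markers in the plural, so P60-N75 may itself be entered.
- **Entry without centring is inferred from silence.** This is true. Calling the model under-specified is fair, but the plain reading is VEP values as recorded.

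**Conclusion.** The concern holds as a matter of specification. As described, the model's VEP coefficient and the treatment-effect shrinkage it produces mix between-child and within-child association. If a between-child association exists in the trial sample and no within-child one does, a test of that coefficient exceeds its 5% level: roughly 6-20% at r of -.2 to -.3, and about 9% to over 50% at r = -.529.

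It is tempting to quote one figure, such as about one in three. The documents support neither that value nor any ceiling. The rate depends on two ICCs and a correlation that they do not give for gamma MSC, and on whether 4 or 8 records per child enter. The direction of the problem is secure; its size is not.

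This is a supporting biomarker analysis. The overall treatment effect, which the Power Analysis names as the main interest, is not affected.

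**What to change.** In Data Analysis, replace the single time-varying VEP covariate with two terms: the child's mean VEP over all visits, and the visit value minus that mean. State that the tracking conclusion rests on the deviation term, with the week-12 change-score correlation as support, and that the child-mean term is reported as the cross-sectional association. Use the split model wherever attenuation of the treatment effect is interpreted, and say whether 4 or 8 records per child enter.

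This takes a sentence or two and no new data. The cost is a tracking estimate that is less precise, and possibly less favourable, than the mixed coefficient, because it no longer draws on differences between children.
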